### 3.4 Objectives

#### Primary objective:

- Evaluate efficacy in terms of PFS from the date of randomization in the study according to Response Evaluation Criteria in Solid Tumors (RECIST) version 1.1 criteria in experimental and control arms.

#### Secondary objectives:

- OS in experimental and control arms from date of randomization,
- Time to failure of treatment strategy (TFTS) in experimental and control arms after randomization,
- PFS rate one year after date of randomization,
- Depth of response (DpR) in terms of reduction of tumor mass in experimental and control arms after of first-line treatment,
- Metastatic resections in experimental and control arms after first-line treatment,
- ORR defined as proportion of patients with partial response (PR) or complete response (CR) as best response in experimental and control arms after start of first-line treatment,
- Safety profile according to the National Cancer Institute's (NCI) Common Terminology Criteria of Adverse Events (CTCAE) version 5.0 criteria in experimental and control arms recorded from date of signature of informed consent.

#### Exploratory objectives (optional):

- To identify driver mutations (e.g., BRAF, PI3k/AKT/mTOR etc.) in patients with PD under cetuximab therapy who remain RASwt in liquid biopsy,

- To compare the efficacy in terms of PFS in patients with conversion to RASwt in both BEAMing (standing for beads, emulsion, amplification, and magnetics) digital polymerase chain reaction (PCR) and Digital Droplet PCR (ddPCR) with those patients showing conversion to RASwt in ddPCR but not in BEAMing.

## 4 Methods of analysis

### 4.1 Hypotheses

Initially, the hypothesis of this study was to show that the difference in PFS at twelve months between the experimental arm and control arm would amount to 20% meaning an increase from 30% to 50% (Hazard ratio = 0.5757). The estimated number of patients screened was 144 and the estimated number of randomized patients was 116.

### 4.3 Statistical analysis

In a first table we give an overview:

- General data such as number of patients, number of participating clinics, and analysis populations (Table 1).

#### 4.3.1 Baseline (anamnesis and one-time-only baseline examinations)

All background data of the patients including demographics, relevant concomitant diseases and medication, and baseline characteristics from pre-screenings which are performed only once will be listed by patient number. Other baseline examinations and laboratory assessments will be summarized together with the same recurring examinations and assessments, respectively. The following listings are planned here:

- Inclusion criteria (Listing 1.1 to Listing 1.3),
- Exclusion criteria (Listing 2.1 to Listing 2.4),
- Eligibility for study participation as well as enrollment for screening phase and randomization (Listing 3),
- Patient characteristics like age, ethnic origin, and gender (Listing 4),
- Initial diagnosis of mCRC (Listing 5.1 to Listing 5.3),
- Relevant diseases according to the 10th revision of the International Statistical Classification of Diseases and Related Health Problems (ICD10) catalog (Listing 6),
- Relevant premedication (Listing 7.1) and concomitant medication (Listing 7.2),
- Baseline echocardiography with left ventricular ejection fraction (LVEF) (Listing 8),
- Tumor, nodes, and metastases classification of malignant tumors (TNM) staging at baseline (Listing 9),
- Baseline coagulation parameters international normalized ratio (INR) and partial thromboplastin time (PTT) (Listing 10),
- Baseline dihydropyrimidine dehydrogenase (DPD) deficiency (Listing 11)
- Baseline hepatitis serology (Listing 12).

#### 4.3.2 Randomization

All enrolled patients with conversion of mutant RAS as estimated centrally by liquid biopsy of cfDNA within the first 4 months (at week 4, 8, 12, or 16) and without PD as determined by CT scan will be randomized at week 8, for patients converting at week 4 or 8, and at week 16, for patients converting at week 12 or 16, directly after the CT scan in a 1:1 ratio to either experimental Arm A (switch arm) or control Arm B. Patients with PD before the randomization will not be considered for randomization.

The randomization into the respective treatment arm will be displayed together with the patient number in each listing.

#### 4.3.3 Recurring examinations and lab assessments

Data gathered through examinations or assessments that are possibly not only performed at baseline such as electrocardiogram (ECG) as well as such that are planned in regular intervals including hematological and blood chemistry lab assessments, pregnancy tests, and tumor marker assessments are given here. An exception is the data obtained from RECIST assessments which belongs to the primary objective. The following listings will be included:

- Performed ECG assessments (Listing 13),
- Determined Eastern Cooperative Oncology Group (ECOG) performance statuses (Listing 14),
- Vital signs such as weight and heartrate (Listing 15),
- Hematological parameters hemoglobin, platelets, leukocytes, and neutrophils (Listing 16),
- Biochemical parameters including specific minerals, gamma-glutamyltransferase (GGT), aspartate aminotransferase (ASAT), alanine aminotransferase (ALAT), and C-reactive protein (CRP) (Listing 17.1 and Listing 17.2),
- Tumor marker parameters carcinoembryonic antigen (CEA) and carbohydrate antigen 19-9 (CA 19-9) (Listing 18),
- RAS mutation analyses performed on tumor tissue with possible detection of Kirsten Rat Sarcoma (KRAS) or neuroblastoma RAS viral oncogene homolog (NRAS) mutations (Listing 19),
- Taken blood samplings for liquid biopsy (Listing 20.1 and Listing 20.2),
- Beta human chorionic gonadotropin ( $\beta$ -HCG) pregnancy tests for women of childbearing potential (WOCBP) (Listing 21).

#### 4.3.4 Study treatment

All data concerning treatment cycles and administered chemotherapeutic treatments will be listed by patient number. The following listings are planned:

- General information such as start date, cycle number, and possible resections (Listing 22.1),
- Specific data on administration of irinotecan (Listing 22.2), folinic acid (Listing 22.3), fluorouracil (5-FU) (Listing 22.4 and Listing 22.5), and cetuximab (Listing 22.6).

These listings will be accompanied by:

- A swimmer plot visualizing the treatment (changes) together with points in time of response for each individual study participant (Figure 1).

#### 4.3.5 Primary objective

For the analysis concerning the primary objective the following three listings are given and considered for PFS:

- RECIST assessments (Listing 23.1) and observation of measurable and non-measurable (Listing 23.2) lesions via computer tomography (CT).

In addition,

- a listing containing PFS, OS, and TFTS (Listing 24)

will be created.

Furthermore,

- a Kaplan-Meier plot for PFS (Figure 2)

will be presented.

#### 4.3.6 Secondary objectives (excluding safety)

Due to the small number of patients neither all secondary objectives will be analyzed, nor full Kaplan-Meier methods will be applied to time-to-event analyses. Only OS, TFTS, and ORR will be considered. The first two named will be shown in the listing containing the primary objective PFS above, and in addition two Kaplan-Meier plots will be presented:

- a Kaplan-Meier plot for OS (Figure 3)
- a Kaplan-Meier plot for TFTS (Figure 4)

The remaining derived variable, ORR, will be given in

- a table displaying responses to study treatment together with ORR (Table 2).

#### 4.3.7 Exploratory objectives

Due to the small number of patients no explorative objective will be analyzed.

#### 4.3.8 End of study treatment, follow-up visits, and end of study

Some data related to end of (study) treatment (EOT) or follow-ups such as AEs or lab assessments will already be listed in the corresponding listings. Remaining data will be included in the following listings:

- EOT with possible new tumor therapy (Listing 25),
- Follow-ups with changes to therapy (Listing 26.1) or performed surgeries (Listing 26.2),
- Date and reason for end of study (Listing 27).

#### 4.3.9 Safety

Regarding the secondary objective safety, all adverse events (AEs) will be ordered by patient number and summarized in the following listings:

- Terminology and timeline of AE together with causality to study treatments as well as possible actions taken (Listing 28.1) and serious or special classification (Listing 28.2).

Optionally, if the number of AEs is sufficient, then the AEs will be analyzed in frequency tables including number of treatment-related AEs, number of AEs that cause permanent treatment discontinuation, system organ class (SOC) and preferred terms (PT) according to the Medical Dictionary for Regulatory Activities (MedDRA). The following tables will optionally be added:

- An AE overview (Table 4.1), number of AEs with respect to MedDRA grouping and NCI CTCAE grading (Table 4.2), and number of patients with AE by maximal grade with respect to MedDRA coding.

SAEs are classified as special if they involve pregnancy or medication error.

#### **4.4 Methods for handling missing data**

Missing data will not be imputed.

#### **4.5 Methods for handling inconsistent data**

Not applicable.

#### **4.6 Methods for handling outliers**

Outliners will not be excluded from analysis.

#### **4.7 Methods for point and interval estimates**

Not applicable.

#### **4.8 Validation of statistical methods**

Not applicable.

#### **4.9 Methods for handling multicenter trial data**

Patients from all study centers will be pooled and tabulated as a single target group.

#### **4.10 Treatment interactions**

There will be no analyses on treatment interactions, but interactions stated in the Summary of medicinal Product Characteristics (SmPC) of each study treatment are beside others:

- Folinic acid may increase the risk of toxicity associated with 5-FU which may be indicated by diarrhea or other gastrointestinal events; both must not be mixed for infusions.
- The combination of cetuximab and fluoropyrimidines such as 5-FU may increase risk of cardiac ischemia or hand-foot syndrome.
- There is no evidence that irinotecan and cetuximab influence each other. Further, the pharmacokinetic of irinotecan is not affected in combination with folinic acid and 5-FU.

#### **4.11 Methods for handling repeated measurements**

No formal repeated measures analysis will be performed.

#### **4.12 Calculation of derived variables**

First, we will clarify some notions regarding trial periods:

Baseline/pre-screening phase (within four weeks before start of treatment): First period of the trial where baseline examinations and baseline lab assessments are performed to confirm eligibility for study participation.

Screening/pre-randomization phase (begins with enrollment of patients and lasts for a maximum of sixteen weeks from start of standard first-line therapy with (m)FOLFIRI): Second period of the trial where conversion to RASwt is monitored and randomization is taking place if (early) conversions are confirmed.

Randomization/study treatment phase (begins with randomization and has a maximal duration of 36 months from start of first-line therapy): Third period where patients are treated with the respective study treatment according to their randomization into experimental Arm A or control Arm B.

Final assessment: Last assessment about four weeks after last treatment administration.

Follow-up: Time from last administration of study treatment until end of study

Pre-cycle: Notion for a treatment cycle in the pre-randomization phase.

Independent of the trial period, each (pre-)cycle has a duration of 14 days. The date of the eighth day of a cycle may be derived from given data as seventh day after the first day of that cycle.

Pre-medication: All medication before first administration of any study treatment, i.e., before first pre-cycle.

Primary and secondary derived variables are defined and calculated as follows:

PFS: Defined as being the time between date of randomization until date of progression according to RECIST v1.1 criteria or date of death from any cause, whichever occurs first. Any change in RAS mutation status without PD according to the RECIST criteria is not considered a PFS event. In patients without a PFS event, PFS will be censored on the last date they were known to be alive and progression-free (last valid tumor assessment) or at the start of a new anti-tumor therapy. Patients becoming eligible for surgery during study treatment will not be censored for PFS at this resection event.

OS: Defined as time from date of randomization until death from any cause. In patients without an OS event, OS will be censored on the last date they were known to be alive.

ORR: Defined as the proportion of randomized patients with CR or PR as best response since start of first-line therapy.

TFTS: Defined as the time from date of randomization to failure of treatment strategy, i.e., treatment discontinuation for any reason, including disease progression, withdrawal of consent, treatment toxicity, patient preference, loss to follow up, or death from any cause.

An AE will be called treatment-related if its occurrence is definitely, probably, or possibly related to the administration of any study treatment.

Note that a year is equal to 365 days, a month is equal to 30.4 days, and a week is equal to 7 days for duration calculations.

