3.1.2 Randomization

All enrolled patients with conversion of mutant *RAS* as estimated centrally by liquid biopsy of cfDNA within the first 4 months (weeks 4 to 16) and without PD as determined by CT scan will be randomized at week 8, for patients converting at week 4 or 8, and at week 16 for patients converting at week 12 or 16 directly after the CT scan in a 1:1 ratio to either experimental Arm A (switch arm) or control Arm B. Patients with progressive disease before the randomization will not be considered for randomization.

The randomization lists will be kept in safe and confidential custody at Alcedis GmbH.

Stratification factors for randomization are:

- Conversion to *RAS*-wt: ≤ 8 weeks vs. > 8 weeks

Randomization of a patient during pre-randomization phase will be performed automatically, at weeks 8 or 16, if centrally assessed *RAS* wild-type in liquid biopsy is documented by the central analysis laboratory before 8 weeks or after 8 weeks, respectively, and there is no disease progression at that time. Randomization result is notified immediately by an automatically generated fax to the investigator.

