3.3.3 Enrolment of Patients

Only patients who meet the inclusion and exclusion criteria are selected and enrolled by online registration.

Online registration is possible 24 hours a day. After the registration form has been saved, a registration number is notified immediately by an automatically generated fax to the investigator.

Patients who are not registered, but sign informed consent and undergo at least some of the selection procedures will be considered screening failures. A record of these patients will be maintained by the study site.

After registration, treatment with FOLFIRI/mFOLFIRI should be instituted within a maximum interval of 14 days.

Patients who are registered but who are not treated within 14 days can be treated under the same patient number after further examinations to make sure that all inclusion and exclusion criteria are still met.

4 Study Treatment

All medications used as study treatment will be prescribed according to routine clinical practice. The drugs will be stored, prepared and administered according to the respective SmPC. Except for cetuximab (Erbilux®, Merck), all other drugs are specified by active substance only within this study.

5 Treatment Plan

5.1 *Treatment Regimen*

The 1st-line therapy is defined as all treatment from start of FOLFIRI / mFOLFIRI (date of the 1st cycle either in the pre-screening or the pre-randomization phase) until progressive disease (PD), unacceptable toxicity, withdrawal of informed consent, loss to follow-up, patient preference, or death.

One cycle consists of 14 days. Drugs will be administered according to each center's routine.

Pre-randomization phase:

Patients will be treated with FOLFIRI. The 5-FU bolus may be omitted at the investigator's discretion to achieve better therapy tolerability (mFOLFIRI).

FOLFIRI (q14d):

- Irinotecan 180 mg/m² iv, 30 - 90 min on day 1
- Folinic acid (racemic) 400 mg/m² iv, 120 min on day 1
- 5-FU 400 mg/m² bolus on day 1
- 5-FU 2400 mg/m² iv over 46 h on day 1-2

OR

mFOLFIRI (q14d):

- Irinotecan 180 mg/m² iv, 30 - 90 min on day 1
- Folinic acid (racemic) 400 mg/m² iv, 120 min on day 1
- 5-FU 2400 mg/m² iv over 46 h on day 1-2

Patients with partial DPD deficiency should receive the first cycle of FOLFIRI with a reduced 5-FU dose. Dose reduction and escalation are at the discretion of the investigator and must be determined in the best interest of the patient.

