8.3 Definition of Measurable Lesion Response Using RECIST Criteria

Version 1.1

Target lesions will be measured in a dimension using the longest diameter is used. The same investigational method must be used throughout.

Complete response (CR): Disappearance of all lesions and appearance of no new lesions.

Partial response (PR): At least a 30% decrease in the sum of the longest diameter of target lesions, taking as reference the baseline sum diameters. No new lesions may occur or individual lesions progress.

Progressive disease (PD): At least a 20% increase in the total of the longest diameters of target lesions, taking as reference the smallest sum on study since the treatment started (this includes the baseline sum if that is the smallest on study) or the appearance of new lesions.

If the marker lesion disappears and the progression of a lesion or the appearance of new lesions is observed elsewhere at the same time, this is also documented as a progressive disease.

Stable disease (SD): Neither a partial nor a complete response in the absence of progression.

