10.1.2 Secondary Variables

- OS, defined as time from date of randomization until death from any cause; OS should be censored, in patients without an OS event, on the last date they were known to be alive.
- TFTS, is defined as time from date of randomization to failure of treatment strategy defined as treatment discontinuation for any reason, including disease progression, withdrawal of consent, treatment toxicity, patient preference, loss to follow up or death from any cause.
- PFS rate 1 year after date of randomization, derived by Kaplan-Meier method (defined as the estimated rate of patients with progression or death from any cause 1 year after date of randomization)
- Depth of response (DpR) in terms of reduction of tumor mass in experimental and control arms, defined as the percentage of tumor shrinkage, based on longest diameters of all target lesions or reconstructed volume, observed at the lowest point (nadir) compared to baseline. The time for DpR assessment varies between patients relating to the individual achievement of maximal tumor shrinkage, which typically occurs 4–6 months after the start of 1st-line therapy. DpR varies between 100% (= all target tumor lesions have disappeared) and 0% (=no change in tumor size) and has a negative value in cases of increased tumor volume.
- Percentage of patients with metastasis resections, defined as percentage of patients with complete resection of primary tumor and metastases (R0-resection), at any time after the start of 1st line therapy until the end of the treatment strategy.
- ORR, defined as the proportion of randomized patients with CR or PR as best response since start of 1st line therapy.
- Safety, defined as all SAEs regardless of causality, and non-serious adverse events according to CTCAE Version 5.0 criteria, that are definitely, probably, or possibly related to the administration of any study treatment, or that cause permanent discontinuation of treatment, recorded from the date of signature of Informed Consent.

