**Table 3: Responses**

Responses according to RECIST v1.1 criteria including Overall response rate (ORR)	Arm A [N, %]	Arm B [N, %]	Total [N, %]
Number of randomized patients			
Most recent response			
Complete response (CR)			
Partial response (PR)			
Stable disease (SD)			
Progressive disease (PD)			
Best response			
Complete response (CR)			
Partial response (PR)			
Stable disease (SD)			
Progressive disease (PD)			
Overall response			
CR or PR (ORR)			

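### Does the by-arm response rate need changing because it counts responses reached before randomisation?

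*SAP*

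**What the plan says.** Protocol 10.1.2 sets out "ORR, defined as the proportion of randomized patients with CR or PR as best response since start of 1st line therapy", and SAP 4.12 repeats it almost word for word: "ORR: Defined as the proportion of randomized patients with CR or PR as best response since start of first-line therapy". Protocol 5.1 fixes the starting point: "The 1st-line therapy is defined as all treatment from start of FOLFIRI / mFOLFIRI", including a first cycle given during pre-screening.

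Partial response is a decrease of at least 30% in the target-lesion sum, "taking as reference the baseline sum diameters" (Protocol 8.3). The baseline scan precedes treatment (Protocol 7.1), and RECIST response is classified every 8 weeks in the pre-randomisation phase (Protocol 7.2).

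Under SAP 4.3.2, patients who convert "will be randomized at week 8, for patients converting at week 4 or 8, and at week 16" for later converters. Protocol 3.1.2 places allocation "directly after the CT scan in a 1:1 ratio to either experimental Arm A (switch arm) or control Arm B". Patients with progression by then are not randomised.

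The Table 3 shell (SAP 5.1) shows most recent response, best response and ORR for Arm A, Arm B and both together. It has no row or note on response status at randomisation. SAP 4.2 reports that enrolment closed with seven patients and that most output will be listings. SAP 4.7 (point and interval estimates) and 4.19 (significance levels) are both marked not applicable.

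**The concern.** A percentage printed under a treatment arm is normally read as something that happened on that treatment. Here part of it may have happened on FOLFIRI before the arms existed. An Arm A patient who reached partial response at week 8 and was then randomised counts as an Arm A responder before receiving any cetuximab. PFS, OS and TFTS all start at randomisation in SAP 4.12, so ORR is the only efficacy variable still analysed that has an earlier origin.

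What would be at stake is interpretation. A reader who takes Table 3 alone could read the two ORR figures as the effect of adding cetuximab.

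**Working it through.** **1. The plan's own figures.** Neither document states a design figure for ORR. The only design calculation is for PFS: HR = ln(0.50)/ln(0.30) = 0.5757. With 58 per arm, uniform accrual over 18 months, exponential PFS and 0.25% monthly drop-out, expected events at 52 months are 107.03, against the stated 107. ORR enters nowhere, so its definition cannot disturb the sample size or the primary analysis.

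**2. Can a response precede allocation?** Yes. RECIST is assessed before randomisation against the pre-treatment sum. With the SAP's 30.4-day month, week 8 is 56/30.4 = 1.84 months and week 16 is 112/30.4 = 3.68 months (nominal times). The protocol says maximal shrinkage "typically occurs 4–6 months after the start of 1st-line therapy". The elapsed shares are 1.84/6 = 31% to 1.84/4 = 46%, and 3.68/6 = 61% to 3.68/4 = 92%. These are shares of the time to the nadir. They are not the probability of a 30% decrease, so they make prior response plausible without measuring how often it occurs.

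**3. Direction and size.** Let q be the share already in response at randomisation, equal in both arms in expectation, and let a and b be the later response rates among the rest in Arms A and B.

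- ORR in A = q + (1 − q)a; ORR in B = q + (1 − q)b.
- Difference = (1 − q)(a − b).

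If cetuximab adds nothing (a = b), the difference is zero at every q, so no arm is favoured. If it adds something, the difference shrinks. With a = 40% and b = 20%, both assumed:

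| q (assumed) | Arm A | Arm B | Difference |
|---|---|---|---|
| 0 | 40% | 20% | 20 points |
| 0.2 | 52% | 36% | 16 points |
| 0.36 | 61.6% | 48.8% | 12.8 points |
| 0.5 | 70% | 60% | 10 points |

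The value 0.36 is the whole-course ORR of 36.0% on FOLFIRI in RAS-mutant patients (Protocol 2.3.2, Table 1). It is a reference point, not an estimate of q.

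**4. Seven patients.** If both arms are populated, the smaller has at most three patients, so one responder moves its ORR by 100/3 = 33 points or more. That holds for a response at any time and describes the sample size, not the definition. If all seven were randomised 4 to 3 (assumed), summing the two binomial distributions over |i/4 − j/3| ≥ 0.25 gives the probability of a chance gap of at least 25 points in prior responders: 0.56 at q = 0.2, 0.54 at q = 0.36 and 0.52 at q = 0.5. A rate this coarse cannot support a comparison under either origin.

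**5. Can the timing be recovered?** Listing 3 gives each randomisation date. Listing 23.1 gives every RECIST assessment with patient, arm, date, overall result and a baseline, pre-cycle or cycle label. SAP 4.12 defines a pre-cycle as belonging to the pre-randomisation phase. Status at randomisation can therefore be read off for each patient. Figure 1, the swimmer plot, adds response times and the change to cetuximab for Arm A, provided its bars start at the first pre-cycle.

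**The case for a change.** The best case for acting is that Table 3 is the only planned table giving efficacy percentages by arm, so it is the one likely to be excerpted. Nobody randomised per protocol after an evaluable scan can have progression as best response, so that row is fixed before allocation. The swimmer plot names no randomisation marker, and Arm B receives FOLFIRI on both sides of allocation, so the plot cannot date Arm B responses against it. One label would cost almost nothing.

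All of that is accurate. The scope is also not settled by the words study treatment in SAP 4.3.6: SAP 4.12 treats pre-cycles as study treatment when defining pre-medication, yet calls the period after randomisation the study treatment phase.

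What stands is that the shell could be clearer. That does not make the plan wrong: the ORR definition itself names its origin, and the listings cover Arm B. Going further, with a count of new responders among those not in response at randomisation, would add a post hoc endpoint after enrolment closed. Its denominator would be three or fewer in the smaller arm, and it would invite the comparison it is meant to prevent.

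**Conclusion.** The observation is correct, but no change is needed. Counting best response from the start of first-line therapy is a declared choice that keeps the usual pre-treatment RECIST baseline. In expectation it shrinks any arm difference by the factor 1 − q and cannot create one. How large q is cannot be known from the documents; the figures above rest on assumed response rates and an assumed split. With at most seven randomised patients and no inference planned on ORR, extra rows would alter no planned result, and a reader can establish the timing of every response from Listings 3 and 23.1. A footnote saying that earlier responses are included is at the authors' discretion. SAP 4.3.6 calls the response table Table 2 while the shell is Table 3; that is a separate clerical slip.

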5.2.1 Permitted concomitant medication / therapy

All treatments that the investigator considers necessary for a patient's welfare may be administered at the discretion of the investigator in keeping with the community standards of medical care. This includes resection of primary tumor / metastases in patients becoming eligible for surgery during study treatment.

Radiotherapy for treatment of bone metastases and drugs for treatment of adverse reactions of study treatment, anthroposophical and homeopathic medicinal products (e.g. mistletoe therapy) are permitted.

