10.1.1 Primary Variable

PFS, defined as being the time between date of randomization until the date of progression according to RECIST v.1.1 criteria or date of death from any cause, whichever occurs first. Any change of *RAS* mutation status without disease progression according to RECIST v.1.1 is not considered a PFS event. PFS should be censored, in patients without a PFS event, on the last date they were known to be alive and progression-free (last valid tumor assessment) or at the start of new anti-tumor therapy. Patients becoming eligible for surgery during study treatment, will not be censored for PFS at this event (resection).

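### ORR has no rule for surgical resection, so a patient with stable disease whose lesions are excised can be tabulated as a responder

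*SAP*

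**What the plan says.** - **Surgery is allowed on treatment.** Protocol 5.2.1 leaves supportive and other necessary treatment to the investigator and adds: "This includes resection of primary tumor / metastases in patients becoming eligible for surgery during study treatment".
- **PFS has a resection rule.** SAP 4.12: "Patients becoming eligible for surgery during study treatment will not be censored for PFS at this resection event". Protocol 10.1.1 says the same.
- **ORR has none.** SAP 4.12: "ORR: Defined as the proportion of randomized patients with CR or PR as best response since start of first-line therapy". Protocol 10.1.2 gives the same definition. Neither sets a cut-off at surgery.
- **The response categories ignore cause.** In Protocol 8.3, CR is "Disappearance of all lesions and appearance of no new lesions". PR needs "At least a 30% decrease in the sum of the longest diameter of target lesions, taking as reference the baseline sum diameters", with no new lesion and no individual lesion progressing. Neither the combination table in 8.5 nor Appendix 17.2 says how to handle an excised lesion.
- **Scanning continues.** Protocol 7.3 and 7.4 schedule CT every 8 weeks in the first year and every 12 weeks after that, until study treatment ends.
- **ORR is kept.** SAP 4.2 reports that enrollment closed with seven patients enlisted. SAP 4.3.6 limits the secondary efficacy analysis to OS, TFTS and ORR. The response table is Table 3 in the mock-ups (4.3.6 cites it as Table 2) and shows best response and ORR by arm and in total.

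**The concern.** ORR is meant to describe what the drugs do to the tumor. A best-response rule that runs at any time from the start of first-line treatment, with no stop at surgery, lets the surgeon's action enter the same count. The trial is open-label and resection is a matter of investigator judgment, so any difference between arms in the use of surgery could look like a difference in drug response.

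A reader of the output would not see it. Table 3 offers only CR, PR, SD and PD, with no row for a patient who can no longer be evaluated for drug response. It also reports the most recent response, which for a resected patient who is rescanned is a post-surgery reading. The swimmer plot legend (Figure 1) shows treatment, response and death, but not surgery.

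**Working it through.** The plan gives no design figure for ORR, and its sample size rests on PFS alone, so there is no ORR figure to reproduce. The check is a reading of the rules followed by simple arithmetic.

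**Step 1: can a post-surgery scan exist?** Yes, if the patient stays on treatment. Protocol 5.2.1 permits the operation and 7.3 and 7.4 keep the CT schedule running. Protocol 7.6 lists no imaging in follow-up, so the route is mainly through patients who continue study treatment after surgery.

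**Step 2: what does the stated rule give for that scan?** Take a patient with stable disease before surgery. Let *s* be the excised target lesions' share of the baseline sum of diameters. Suppose the remaining target lesions are at their baseline size and nothing new appears.
- The decrease from baseline is then *s*. If *s* is at least 30%, the PR threshold in 8.3 is met.
- If all target lesions are removed and non-target lesions persist, the 8.5 table combines CR in target lesions with SD in non-target lesions and returns PR.
- If all lesions are removed, the CR wording in 8.3 is met.

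**Step 3: does anything stop the scan from entering ORR?** The PFS rule does not reach ORR, and the ORR definition has no end date. Under the literal text the patient's best response becomes CR or PR.

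**Step 4: how much does one such patient move ORR?** The shift is 100/*n* percentage points, where *n* is the number of randomized patients in the denominator. SAP 4.2 gives seven as enlisted and does not say how many were randomized. Patients without conversion leave before randomization (Protocol 3.1), so smaller values are also shown.

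| Denominator | Shift per patient |
|---|---|
| 7 (all enlisted patients randomized) | 100/7 = 14.3 points |
| 6 | 100/6 = 16.7 points |
| 5 | 100/5 = 20.0 points |
| 58 (planned arm size, Protocol 10.4) | 100/58 = 1.7 points |

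Within an arm of the actual trial the shift is 100 divided by that arm's size, which the documents do not give. A corrected ORR cannot be computed, because the number of resected patients is not reported.

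**The case against.** The strongest reply is that silence is not an instruction. Response is assigned under RECIST v1.1, which the protocol cites as its source (8.1) and which heads SAP Table 3. Section 8.3 is a short summary, and the full criteria might settle the matter; they are not part of these documents, so that cannot be resolved here. Classification is not purely mechanical either: Listing 23.1 carries an overall assessment, a consultation flag and a comment field for each staging.

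The consequence is also limited. The SAP sets no significance level (4.19) and no estimation method (4.7), and Protocol 10.3 already made everything except the primary log-rank test exploratory. RECIST dates, lesion sizes and metastasis-resection dates are all listed, so recorded cases can be traced one by one.

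Most of this stands as a limit on size. It does not close the gap: the plan does not ask anyone to match the surgery listings to the RECIST listings, and Table 3 alone would not reveal the problem.

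Four stronger readings might be inferred, and the documents do not support them.
- **That resected lesions do count as response.** Nothing directs that; they can be counted.
- **That depth of response is inflated in the final analysis.** The protocol's definition uses the nadir without a surgical cut-off, but SAP 4.3.6 does not analyse that endpoint.
- **That a resected patient is counted twice, in ORR and in the resection endpoint.** The final SAP drops the resection endpoint, and the protocol version requires complete (R0) removal of primary and metastases.
- **That a percentage bias between arms can be stated.** Neither the number of resections nor the split between arms is given.

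**Conclusion.** The point holds as a defect in the stated ORR rule. An any-time best response, combined with permitted resection and continued scanning, can credit an excised lesion as a drug response in a table that the SAP keeps and splits by arm.

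Its size is conditional. It is zero if no patient was resected on treatment and rescanned. Otherwise each patient whose CR or PR rests only on post-resection scans moves the total ORR by about 14 points, assuming all seven enlisted patients were randomized, and by more if fewer were. At the planned 58 per arm the figure would have been 1.7 points in that arm. The effect is confined to a descriptive secondary result. PFS has its own resection rule, and the primary endpoint and sample size are untouched.

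**What to change.** - **SAP 4.12:** state that best response for ORR uses only tumor assessments before the first recorded resection of a tumor lesion, and that later assessments are used for progression only. Protocol 10.1.2 should be read the same way.
- **SAP Table 3:** add a footnote with the number of patients whose CR or PR was first seen after resection.
- **SAP Figure 1:** mark resection dates on the swimmer plot.
- **Depth of response:** apply the same cut-off only if that endpoint is ever reported.

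The dates come from Listings 22.1, 25.1 and 26.2. This needs some manual work. The type of surgery has to be checked by hand against the lesions in Listing 23.2. Listings 22.1 and 26.2 cover metastases only, and the surgery fields in 22.1 come from treatment cycles after randomization, although ORR runs from the start of first-line treatment. Any resection in the pre-randomization cycles, or of the primary tumor, must therefore be looked for separately. With at most seven patients this is a small task.

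The downside is that a true drug response first seen after a partial resection is not credited. The Table 3 footnote keeps such patients visible.
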